### **Sample Size Estimates and Power Calculations**

The database for FY 2010/11 shows that 386 clinics fit the criteria with 89 sites available for arms 1-2 and 297 available for the comparison group. The mean number of female clients aged 21-29 years seen at the eligible clinics was 560 and the mean number of cytology specimens, colposcopic examinations and LEEP/cryoprocures for this age group was 297, 40, and 4, respectively. In 2012, the mean cytology interval was 19 months. Very few clinics had an interval >30 months. There were no differences for any of the above variables between those

sites eligible for intervention and those for comparison. These numbers have not changed significantly in the past 2 years and will be updated for the baseline assessment.

After enrolling 7 sites into each arm, we estimate that we would have approximately 2800-3500 women aged 21-29 years in each arm. For each arm, baseline cytology rate in this age group would be approximately 50%, rate of colposcopy procedures for those who had cytology would be 13%, and rate of LEEP/cryotherapy procedures for those referred to colposcopy would be 10%.

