Parallel calculations for the secondary colposcopy outcome also are based on between-arm comparison of changes in three-month colposcopy rates from baseline levels, and assume that approximately 50% of women will receive cytology at baseline and follow-up in the control group, and that colposcopy rates will also remain unchanged at 13%. We also assume that the intervention-related reduction in cytology will result in approximately 20% fewer women eligible for colposcopy at follow-up. Based on similar assumptions about intracluster correlation and loss to follow-up, results indicate that with the planned total sample size of 9030, we will retain at least 80% power to detect an intervention-related reduction in colposcopy rate as small as 8% at the 5% (one-sided) significance level. Due to our conservative assumptions, we should have sufficient power to detect even smaller intervention-related effects in analyses adjusting for baseline characteristics.

We did not perform calculations for the testing interval length and LEEP outcomes because of the lack of preliminary data on their potential variability within and between clinics.

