**b) To increase average length of cervical cytology testing among women under 30 years of age**

**Pre:** cervical cytology test interval among women who received two CC tests from same provider (analysis limited to providers who have been in program at least 36 months)

**Post:** cervical cytology test interval among women who received their second CC test 3-15 months after the intervention started.

**c)** To decrease the number of LEEP and cryotherapy procedures in women under 30 years of age with abnormal cytology.

**Pre:** Rate of women 21-29 years of age who receive LEEP or cryotherapy over total number of women 21-29 years of age in quarter before intervention started.

**Post:** Rate of women 21-29 years of age who receive colposcopy or LEEP or cryotherapy over total number of women 21-29 years of age in 3-6, 9-12, and 15-18 months after intervention started.

**d)** To decrease the number of colposcopy procedures in women 21-24 years of age with abnormal cytology.

**Pre:** Rate of women 21-24 years of age who receive colposcopy over total number of women 21-24 years in quarter before intervention started.

**Post:** Rate of women 21-24 years who receive colposcopy over total number of women 21-24 years of age in 3-6, 9-12, and 15-18 months after intervention started.

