The primary outcome measure will compare the observed within-clinic changes in cervical cytology testing rates between intervention and comparison groups using a t-test accounting for clinic-level clustering. We will use the same approach to test differences between each of the APP and APP + PCA and the comparison groups. Tests will be adjusted for multiple comparisons. Secondary endpoints include examining the interval between tests for women who received two cervical cytology tests from the same provider and the decrease in the number (and percent) of women receiving colposcopy procedures and LEEP or cryotherapy procedures. These will be analyzed using a similar approach as adopted for the primary endpoint. Patient satisfaction surveys will be administered to all women evaluated and compared between interventions and the controls. Because most available data is on the clinic level, we will have limited opportunities to analyze patient-level data. However we will be able to conduct supplementary analyses to investigate the possible impacts of between-arm imbalances in clinic level characteristics such as racial/ethnic composition, age distribution, descriptors of lab procedures, additional app or educational materials that are not part of the assigned intervention, and cervical cancer screening educational activities. Prior to starting the intervention and during the study, administrators and physicians at each clinic site will be asked about possible confounding variables at their clinic.

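### Outcome (c) counts different procedures before and after the intervention, and its three-month windows hold too few LEEP/cryotherapy events to inform

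*Combined protocol and SAP*

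**What the plan says.** Sample Size Estimates and Power Calculations introduces its clinic data with "The database for FY 2010/11 shows that 386 clinics fit the criteria". It continues: "The mean number of female clients aged 21-29 years seen at the eligible clinics was 560". The mean counts of cytology specimens, colposcopies and treatment procedures follow, ending "LEEP/cryoprocures for this age group was 297, 40, and 4, respectively". The same section plans seven clinics per arm with an average of 430 women each. It takes rates of 50% for cytology, 13% for colposcopy among those with cytology, and 10% for LEEP/cryotherapy among those referred to colposcopy. On power for this outcome it says only "We did not perform calculations for the testing interval length and LEEP outcomes", for want of data on variability within and between clinics.

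Under Data Analyses, the aim of outcome (c) is fewer LEEP and cryotherapy procedures. The baseline measure is the proportion of women aged 21-29 with LEEP or cryotherapy in the one quarter before the start. The follow-up measure is the proportion with colposcopy, LEEP or cryotherapy "in 3-6, 9-12, and 15-18 months after intervention started". Of the secondary endpoints the plan says "These will be analyzed using a similar approach as adopted for the primary endpoint"; for the primary endpoint that approach is a t-test on within-clinic change that accounts for clinic-level clustering. The text does not say whether the three follow-up windows are tested one by one or combined.

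**The concern.** A change from baseline has meaning only if the same thing is counted at both ends. With colposcopy added at follow-up only, about ten of every eleven follow-up events would be colposcopies. The result would say little about overtreatment, and it would overlap with outcome (d), which covers colposcopy in women aged 21-24.

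Even with the definition repaired, LEEP/cryotherapy is rare and the windows are short. Months 6-9 and 12-15, and all claims before the single baseline quarter, go unused for this outcome. Excisional procedures are named in the study objectives and in the research question. A null result from so few events could be misread as evidence that the interventions do not affect overtreatment.

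**Working it through.** **Inputs.** From Sample Size Estimates and Power Calculations: 560 women, 297 cytology specimens, 40 colposcopies and 4 LEEP/cryotherapy procedures per eligible clinic; planned 7 clinics per arm and 430 women per clinic; rates 50%, 13% and 10%. From Data Analyses: one quarter before; months 3-6, 9-12 and 15-18 after. Assumed: the counts cover one fiscal year; reduction of 50%; two-sided 5% level; Poisson counts; equal denominators in each quarter.

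**The plan's own rates reproduce.** 297/560 = 53%; 40/297 = 13.5%; 4/40 = 10%.

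**Definition mismatch.** Before: 4/4 = 1 event per clinic-quarter. After, as written: 40/4 + 4/4 = 10 + 1 = 11. If women who have both are counted once, the figure lies between 10 and 11.

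**Event counts with LEEP or cryotherapy in both periods.**
- Eligible-clinic mean: 4/4 = 1.0 per clinic-quarter, so 7 per arm-quarter.
- Planned clinic size: 430 × 0.50 × 0.13 × 0.10 / 4 = 2.795/4 = 0.70, so 4.9 per arm-quarter.
- If the 50% and 13% are true three-month rates, as the power calculations treat them: 2.8 per clinic-quarter.

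**Power of the planned test.** Simulation: 7 v 7 clinics, Poisson counts, two-sample t-test with 12 df on each clinic's change in rate, 50% reduction in one arm.

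| Events per clinic-quarter | 1 quarter v 1 quarter | 1 quarter v mean of 3 | 12 months v months 3-18 |
|---|---|---|---|
| 0.7 | 8% | 10% | 21% |
| 1.0 | 10% | 12% | 27% |
| 2.8 | 19% | 25% | 62% |

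- Complete elimination of the procedures, one quarter v one quarter: about 21% at 0.7 and 29% at 1.0.
- Significance level of 2.5%, to allow for two comparisons: 4-5% power for a halving, one quarter v one quarter, at 0.7 and 1.0.
- No true effect: the t-test rejects in 4.7-4.8% of runs at 0.7 and 1.0, and in 4.6% at 1.0 with a between-clinic coefficient of variation of 0.5. It keeps its error rate despite many zeros (exp(-1.0) = 37% and exp(-0.7) = 50% of clinic-quarters).
- Averaging three follow-up quarters helps little because the one baseline quarter dominates the variance.

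**Precision.** The variance of the difference in mean change is (2λ/q_pre + 1.5λ/q_post)/7, with λ events per clinic-quarter and q the number of quarters. The factor 1.5 is 1 for the comparison arm plus 0.5 for the halved arm. The 95% half-width uses t = 2.179.
- λ = 1.0, one v one: √(3.5/7) = 0.707; × 2.179 = 1.54, or 154% of the baseline rate.
- λ = 1.0, four v five quarters: √((0.5 + 0.3)/7) = 0.338; × 2.179 = 0.74, or 74%.
- λ = 0.7: 184% falls to 88%.

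**Log-rate formula (optimistic: arm totals, Poisson variance, no clinic-level variance).** SE² = 2/E_pre + 1/E_post + 1/(0.5 E_post), with E the events per arm.
- λ = 1.0, E = 28 and 35: SE = √(0.0714 + 0.0286 + 0.0571) = 0.396; power Φ(0.693/0.396 − 1.96) = 42%. One v one quarter: 13%.
- λ = 0.7, E = 19.6 and 24.5: SE = 0.474; power 31%. One v one quarter: 10%.

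**The case against.** LEEP/cryotherapy is one of several secondary endpoints, and the plan openly says that it was not sized. The extra word colposcopy is probably a drafting slip, since the aim and the baseline measure omit it. Both points stand. They limit the weight of the finding, but the definition still has to be settled before the outcome data are seen.

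The time base is also open. The clinic counts follow a statement about one fiscal year but are not labelled as annual, and the power calculations use the rates as quarterly. On the quarterly reading there are 2.8 events per clinic-quarter and power for a halving is 19-25%. That is better but still low.

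A reader might infer that the many zero counts make the t-test a poor method here. The arithmetic does not support that: the test holds its 5% level, and a count model on the same short windows would face the same shortage of events. A reader might also infer that the three follow-up windows will be tested separately, which the plan does not say; the averaged version is therefore shown too. Leaving out months 0-3 may be a deliberate run-in and is not criticised.

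**Conclusion.** Outcome (c) needs correcting on both counts. The mismatch in definition follows directly from the text and rests on no assumption; only its size (about 1 against 11 events per clinic-quarter) uses the reported means.

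The low information rests on reading those means as annual totals, on an assumed 50% reduction and on Poisson variation. Under these, power is about 8-10% for single quarters and 10-12% with the follow-up quarters averaged.

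It would be too strong to say that pooling rescues the outcome. With 12 months before and months 3-18 after, power is 21-27% by t-test and 31-42% by the optimistic formula. Using 36 months before would give about 32-43% by t-test. Only if the rates are truly quarterly would power reach 62% with 12 months before, or about 85% with 36. The dependable gain is that the interval roughly halves in width. As this is a secondary outcome, the change is advisable and does not threaten the primary analysis.

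**What to change.** For outcome (c):
- Count LEEP or cryotherapy in both periods, in line with the stated aim. Leave colposcopy to its own outcome.
- Pool at least 12 months of claims before the start. The eligibility criteria already use three years of claims, so the data exist. Use all of months 3-18 after.
- Define the denominator identically in both periods, for example women seen summed over quarters, because the periods differ in length.
- Compare clinic-level changes with a method that respects seven clinics per arm: a clinic-level t-test or permutation test, or a count model with an offset for women seen, an arm-by-period term and clinic-level variance.
- Report the rate ratio with its 95% interval, and label the outcome descriptive.
- State whether the reported clinic counts and rates are annual or quarterly.

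Cost: slightly more analysis work, with no new sites or data collection. The windows for this outcome will differ from those for cytology, and the report should say so.

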## ANALYTIC METHODS

### Research Question

Does provision of patient and provider educational materials increase adherence to cervical cancer screening guidelines (increase in screening interval and decrease in diagnostic and excisional procedures) in women under age 30?

### Choice of Outcomes

Family PACT claims data will be used to examine by age, the number of and average interval between cytology specimens, and the number of cervical procedures. However, we hypothesize that the group with both interventions (physician plus patient interventions) will be more successful in guideline adherence than physician interventions alone or the comparison group (no intervention).

### Missing Data

Missing data may arise at several points in the study. Clinicians have six months to submit a claim for reimbursement after the last date of service. The claims data are 90% complete at the last date of service and 99% after six months of the last date of service. We will feel confident that we can conduct the statistical analysis in years 1 (pre-intervention) and 3 (post-intervention) with a 90% complete dataset but will rerun the models in year 2 (interim data analysis) to confirm the results with the 99% complete dataset for pre-intervention and will rerun the end of study results at 6 months post end of study. Patient information may be missing on the examination or intake form or from the patient satisfaction survey or patients may drop out or be lost to follow-up in the study. The randomness of this information will be examined to ensure that its missing-ness is not related to any patient, clinic, or intervention arm factors. In addition to this, lab results may be contaminated or lost entirely. The pattern of unusable lab results will be analyzed to identify any clinic or intervention arm bias. Reasons for missing data will be collected and tabulated.

### Data Analyses

Outcomes to be evaluated within and between intervention arms are based on the specific research aims:

**a) Decrease the rate of cervical cytology testing among women ages 21-29 years of age**

**Pre:** Rate of women 21-29 years of age who received cervical cytology tests over total number of women 21-29 years of age in quarter (3 months) before start of intervention

**Post:** Rate of women 21-29 years of age who received cervical cytology tests over total number of women 21-29 years of age in months 3-6, 9-12, and 15-18 after intervention started

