Sample size calculations for the primary endpoint (rate of cytology testing) are based on a pairwise comparison of observed changes from baseline in clinic-specific three-month testing rates between intervention study arms (APP or APP+PCA) and the control arm, using a t-test adjusted for clustering on the clinic level. The baseline rate in control clinics is assumed to be approximately 50%, consistent with the preliminary data presented above. Assuming that there will be no observed change in rates for control clinics during the testing period, our expected sample size of 9030 (i.e. 3010 per arm, seven clinics per arm, and an average of 430 women per clinic) will be sufficient to provide 90% power to detect a between-arm difference as small as 16% as significant. This calculation assumes a quite conservative value for the intracluster correlation of outcomes within clinics of 0.07, and is based on a 1% significance level to account for the fact that there will be two pairwise comparisons with the control arm (i.e. one per intervention arm). Accounting for as much as 10% missing data on testing rates, we will still retain more than 90% power to detect differences of this magnitude or larger between arms as significant at the 5% level. We should also retain adequate power to conduct additional sensitivity analyses investigating the possible confounding influence of clinic-level descriptors (e.g. race/ethnicity and age distribution) on observed results. Finally, we note that our proposed analysis that will account for within-clinic paired observation of outcome rates and adjust for baseline covariates will likely yield more power than the conservative estimates made above. Although the study is not powered to detect significant differences between intervention groups, a similar calculation for the comparison between the APP and APP+PCA groups indicates that we retain at least 70% power to detect a difference in observed changes in testing rates as small as 15% as significant at the 5% level.

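### The primary cytology rate has three post-intervention windows but no primary window or combining rule, and the promised multiplicity adjustment is unspecified

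*Combined protocol and SAP*

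**What the plan says.** All references are to the Combined protocol and SAP.

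- **Data Analyses, outcome (a).** The baseline rate is taken "in quarter (3 months) before start of intervention". The post rate is taken "in months 3-6, 9-12, and 15-18 after intervention started". No window is called primary, and no average, repeated-measures model or success rule is given.
- **Data Analyses, primary outcome paragraph.** The primary analysis is a t-test on within-clinic change in the testing rate, allowing for clustering, with each intervention arm set against the comparison group. The paragraph promises a multiplicity adjustment but gives no method, family of tests or overall level.
- **Sample Size Estimates and Power Calculations.** The outcome is the change in a three-month rate, with the post quarter not identified. The calculation "is based on a 1% significance level to account for the fact that there will be two pairwise comparisons with the control arm". The sentence on missing data uses another level for the same comparison: "we will still retain more than 90% power to detect differences of this magnitude or larger between arms as significant at the 5% level".
- **Progress Review.** Stakeholders meet twice a year, see interim and final outcome data, and may change the protocol or the interventions. The Missing Data section also mentions an interim analysis in year 2.

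**The concern.** A t-test on within-clinic change takes one number per clinic, but the outcome definition yields three. The primary analysis therefore cannot be run without a decision that the plan does not record: one window, all three, any one of them, or an average. Outcome data are reviewed while the trial runs and the protocol may then be changed, so that decision could be made with results in view.

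Two further things are at stake. The family of primary tests is undefined: it is two if the windows are combined or one is chosen, and six if each window is tested for both arms. Only two is reflected in the reason given for the level. Also, with seven clinics per arm precision is scarce, and an analysis that uses one post window leaves two thirds of the post-intervention measurements out of the primary test.

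**Working it through.** **Inputs from the documents.** Seven clinics and 3010 women per arm (430 per clinic), intracluster correlation 0.07, control rate 50%, a difference of 16 points (50% to 34%), 1% level, one baseline quarter and three post windows. Sidedness of the primary test is not stated; I take two-sided.

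**Assumptions of mine.** 150 women per clinic-quarter (range shown in step 4), and the same correlation ρ between clinic effects in any two periods, tried from 0.3 to 0.9.

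**1. The plan's own power figure.** The plan states "90% power to detect a between-arm difference as small as 16% as significant".
- Design effect = 1 + (430 − 1) × 0.07 = 31.03. Effective n = 3010 / 31.03 = 97.0 per arm.
- Power at 1% two-sided is 37.4% by the two-proportion z-test and 27.6% by a t-test with 12 df. At 5% two-sided the z-test gives 61.9%.
- The 90% does not reproduce from these inputs. At 1% it would need an intracluster correlation of about 0.022 or less, or a clinic-level pre-post correlation of about 0.83 in a change-score analysis. The documents give neither.

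This is a separate matter. It is relevant here only because it shows that precision cannot be spared.

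**2. How many tests.** Two arms × one combined or chosen window = 2. Two arms × three windows = 6.

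**3. Family-wise error.** The bound is (number of tests) × (level per test). The simulated values are for null trials with 3 arms × 7 clinics × 4 periods, a shared baseline and control group, and 12-df t-tests.

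| Tests | Level each | Bound | Simulated |
|---|---|---|---|
| 6 | 1% | 6% | about 5.2–5.4% |
| 6 | 2.5% | 15% | about 12% |
| 6 | 5% | 30% | about 22% |
| 2 (one window) | 1% | 2% | about 1.9% |
| 2 (averaged windows) | 2.5% | 5% | about 4.6% |

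The results hardly move with ρ. For six independent tests at 1%, 1 − 0.99⁶ = 5.85%.

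**4. What averaging gains.** Let B = 0.07 × 0.25 = 0.0175 (between-clinic variance) and S = 0.93 × 0.25 / 150 = 0.00155 (sampling variance of a clinic-quarter rate).
- Variance of one window minus baseline: 2 × [B(1 − ρ) + S].
- Variance of the mean of three windows minus baseline: (1 + 1/3) × [B(1 − ρ) + S].
- Ratio: (4/3) / 2 = 2/3, a reduction of one third whatever ρ and the number of women are.

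At ρ = 0.6 the bracket is 0.0070 + 0.00155 = 0.00855, so the variances are 0.0171 and 0.0114. The standard error of the difference between arms is √(2 × 0.0171 / 7) = 0.0699 for one window and √(2 × 0.0114 / 7) = 0.0571 for the average. The noncentrality for 16 points is 0.16 / 0.0699 = 2.29 and 0.16 / 0.0571 = 2.80. Against a critical value of 3.05 (12 df, 1% two-sided), power is about 28% and 44%; simulation gave 27% and 43%. The closeness to the 27.6% in step 1 is a coincidence of inputs.

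Simulated power for 16 points at 1%, 150 women per clinic-quarter:

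| ρ | One window | Mean of three |
|---|---|---|
| 0.3 | 15% | 25% |
| 0.6 | 27% | 43% |
| 0.9 | 73% | 90% |

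Range for the assumed 150: with 430 / 4 ≈ 108 women per clinic-quarter, the same formula at ρ = 0.6 gives 26% and 41%; with all 430 seen every quarter, 32% and 50%. The absolute power depends on the assumption; the one-third reduction in variance does not.

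**The case against.** The strongest reply is that the plan never says it will run six tests. A reader might infer six from three windows and two arms, but no section says that each window will be tested separately. The analysis section speaks of a single primary outcome measure, and the power section counts two comparisons, which fits one contrast per arm. The plan also promises a multiplicity adjustment. All of this stands, so six is an upper limit and not a description of the plan.

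A reader might also infer that the false-positive rate is badly inflated. At the 1% level of the primary power calculation it is not: 1% is stricter than two comparisons need (0.05 / 2 = 2.5%), and even six tests come to about 5%. The 12% and 22% figures require levels that the primary power calculation does not use. The 5% level does appear in the missing-data sentence, so the documents do not exclude it, but the promised adjustment argues against an unadjusted 5%.

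The three windows might instead be read as one rate over all the listed months. That would leave two tests, but it would set a nine-month rate against a three-month baseline, whereas the power section refers to three-month rates throughout. The reading is possible and unconfirmed, which is the difficulty.

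Finally, averaging is partly a matter of preference. Naming one window, or testing windows in a fixed order, would also remove the later choice. That is fair, but a single named window gives up the gain in precision.

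**Conclusion.** The point holds as an undefined primary time point, with an unspecified multiplicity family attached to it. It does not hold as a finding of serious error inflation: at most about 5% to 6% at 1% per test, if all six tests were run.

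The weight lies on two consequences. The window or success rule could be settled after interim outcomes are known; the documents allow this, though nothing in them shows that it is intended. And a single-window analysis has a change-score variance one and a half times that of the three-window mean. The variance result rests on equal correlation between periods and similar numbers of women in each window. The power figures rest also on the assumed 150 women per clinic-quarter and the plan's intracluster correlation of 0.07.

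A reader might credit the fix with the further power from testing at 2.5% instead of 1%. That comes from the level alone and is open to any single pre-specified window, so it is not counted here; the comparisons above are all at 1%.

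**What to change.** Add one paragraph to the Data Analyses section, dated before any post-intervention outcome is seen:

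- The primary measure for each clinic is the mean of its three post-window rates minus its baseline-quarter rate. Each rate stays a three-month rate, so the contrast is like for like.
- Each intervention arm is tested against the comparison group at a family-wise 5% for two comparisons, for example 2.5% each (simulated family-wise error about 4.6%). State the method, the family, the level and the sidedness, and use the same level throughout the power section.
- The three separate windows are reported as a descriptive time course with confidence intervals.
- Outcomes (c) and (d) use the same three windows and should follow the same rule.

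The cost is wording only; no clinics or data are added. The downside is that an effect present only late is diluted in the average. If the sponsor expects that pattern, naming the last window as primary also closes the gap, at the price of the lost precision.
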